1.2 Version History

Version 2.0 of the Primary SAP provides additional detail on analytic strategies to address protocol deviations involving eligibility, enrollment, or randomization and missing or unscorable data based on SMC request. A summary of major changes is as follows:

- (1) Defines analysis populations and specifies their use in primary, secondary, and supplementary analyses;
- (2) Provides detail on existing individual-level supplementary analyses, and adds new supplementary analysis for two-component, rather than three-component, mental health composite measure;
- (3) Adds new supplementary analyses to investigate bias due to missing or unscorable data and eligibility, enrollment, or randomization deviations;
- (4) Defines unscorable UCLA PTSD-RI assessments and specifies their handling in analysis, including which analyses will follow complete case and imputation strategies;
- (5) Updates reporting to include number and nature of eligibility, enrollment, and randomization errors and reflect updated data collection.

2 Study Overview

2.1 Overview of Study Design

IMPAACT 2016 is a multi-site, two-arm, individually randomized group trial (IRGT) preceded by Focus Groups and Pilot Testing to adapt the intervention to the local context. The purpose of the study is to evaluate whether an Indigenous Leader Outreach Model (ILOM) of trauma-informed cognitive behavioral therapy (TI-CBT) is associated with improved mental health outcomes and antiretroviral therapy (ART) adherence among youth living with HIV. The study population consists of 15-19 year old youth living with HIV and mental health distress, along with their caregivers (if available and agreed to by the associated youth participant).

There will be approximately 192-256 youth participants (96-128 per arm), plus their caregivers, in the Randomized Trial. Youth participants will be randomized in a 1:1 ratio to one of two study arms (TI-CBT Intervention or Discussion Control) in a parallel-group design. Randomization will be stratified by gender to assure approximate balance between study arms. Each arm will have 12-16 groups with an average of eight youth participants per group (range 6-10). Youth participants' caregivers will be assigned to the same arm as their youth participants. For accrual, as a site recruits enough youth to form two groups, the youth will be randomized on the day of enrollment to either TI-CBT or Discussion Control.

Prior to the Randomized Trial, Focus Groups comprised of 5-8 youth participants and 5-8 caregiver participants will be conducted at selected sites. All sites will also conduct a Pilot Test with up to eight youth participants and up to eight caregiver participants. There will be no data analysis of the Focus Groups or Pilot Tests, which are therefore not included in this SAP.

Youth participants in the Randomized Trial will have the following study visits: screening (determine eligibility), pre-entry (collect baseline assessments), entry (randomization and enrollment), immediately post-last group session (IPL), 6-month follow-up, 12-month follow-up/exit visit. Caregiver participants will have the following study visits: screening/entry (may occur same day), IPL, 6-month follow-up, 12-month follow-up/exit visit. CASI-administered assessments will occur for all participants at the other visits; youth participants will also provide blood and hair samples. Youth participants will have six group sessions after entry while caregivers will have two. All participants will have a 6-month booster group session after the 6-month follow-up assessment.

2.2 Hypothesis

The TI-CBT Intervention will result in reduced symptoms of depression, anxiety, and/or traumatic stress compared to the Discussion Control at six months.

2.3 Study Objectives

This Primary SAP addresses the following primary and secondary objectives listed in the study protocol which will be included within the primary manuscript. Other study objectives in the protocol will be addressed in subsequent analysis plans.

The study objectives below will be analyzed under a superiority framework. As the primary completion date at 6 months precedes the end of follow-up at 12 months, the following objectives will only be considered prior to, or at, 6 months.

2.3.1 Primary Objective

1. Evaluate whether a TI-CBT Intervention is associated with improved depression, anxiety, and/or traumatic stress symptoms for youth living with HIV compared to a Discussion Control at six months [Objective 2.1.1].

2.3.2 Secondary Objectives

1. Evaluate whether a TI-CBT Intervention is associated with improved depression, anxiety, and/or traumatic stress symptoms for youth living with HIV compared to a Discussion Control following the last group session (at IPL) and at 12 months [Objective 2.2.2].
2. Assess whether a TI-CBT Intervention is associated with improved ART adherence (hair samples, self-report) and viral suppression (HIV RNA plasma) for youth living with HIV compared to a Discussion Control following the last group session (at IPL) and at 6 and 12 months [Objective 2.2.3].
3. Compare the rates of all targeted adverse events between a TI-CBT Intervention and a Discussion Control for youth living with HIV [Objective 2.2.8].

2.4 Overview of Sample Size Considerations

The proposed sample size for the Randomized Trial is 192-256 youth, expected to be enrolled from eight sites in four countries in sub-Saharan Africa. The sample size was chosen to provide 80% power to detect an effect size of 0.42-0.62 standard deviations between arms at 6 months, assuming an average group size of 8 and an intraclass correlation (ICC) range of 0.05 to 0.15.

This is a superiority study and the sample size was chosen to provide 80% power with a two-sided $\alpha=0.05$ to detect a clinically important difference in the primary efficacy measures between study arms, allowing for a 10% loss to follow-up between study visits. The team will use two-sided tests to ensure power to detect differences between groups in both directions, but the hypothesis is that TI-CBT groups will lead to better mental health than the Discussion Control groups.

Further details on the assumptions and sample size calculations are provided in protocol Section 9.4.

2.5 Overview of Formal Interim Monitoring

An independent IMPAACT Study Monitoring Committee (SMC) will review this study regularly, following policies described in the IMPAACT Manual of Procedures. Once enrollment has started, there will be an SMC review to monitor accrual 6 months after the first participant is enrolled in the Pilot Study. Full SMC reviews will occur annually after the start of enrollment. The intervening 6-month reviews will focus on study milestones, accrual, fidelity to study interventions, and a qualitative discussion of feasibility. *Ad hoc* reviews will be scheduled as needed if any safety issues or concerns arise.

There will be no interim analysis of study outcome measures. However, there will be interim analyses to check the validity of the assumptions used for sample size calculations, to determine if it is necessary to increase the number of participants to ensure adequate power for the primary study objectives. Power decreases as the intra-cluster correlation (ICC, measure of correlation between treatment group members) increases. An interim evaluation of the ICC will occur once five groups in each Randomized Trial study arm have completed their six sessions, to see if it is greater than 0.15 (the largest value for which the selected sample size provides 80% power to detect acceptable minimum differences). An evaluation of loss to follow-up will occur when five groups/arm have reached the end of the window for their 6-month follow-ups. Both of these analyses will be presented to the SMC only, in a Closed Report. When five groups/arm have reached the end of the window for their 6-month follow-ups, the proportion of enrolled participants in the Randomized Trial who do not have six-month follow-up assessments will be assessed to see if it exceeds 10%. At each of these milestones, the protocol statistician will provide an interim analysis report including relevant data and assessment outcome, with a recommendation to maintain or increase the sample size for the SMC to review and make a final determination. If the SMC determines that the ICC or loss to follow-up rate require a sample size recalculation, the team will work with a blinded non-protocol statistician to determine the new sample size.

3 Outcome Measures

The study primary and secondary outcome measures used to address the study's primary and major secondary objectives are listed in Protocol Section 9.2 Table 4.

3.1 Primary Outcome Measures

The primary outcome measures used to address the study's primary objective are the following measures of mental health at 6 months after entry:

1. Patient Health Questionnaire-9 score (PHQ-9, measure of depression);
2. General Anxiety Disorder-7 score (GAD-7, measure of anxiety);
3. UCLA Post-Traumatic Stress Disorder-Reaction Index (UCLA PTSD-RI, measure of PTSD);
4. Composite mental health measure (PHQ-9, GAD-7, and UCLA PTSD-RI scores will be standardized and then summed).

3.2 Secondary Outcome Measures

The secondary outcome measures used to address the secondary objectives listed in Section 2.3 are as follows.

Mental Health Measures

The secondary mental health measures will be the same measures as in Section 3.1 above but assessed at the immediate post-last group session (IPL).

ART Adherence Measures

The following ART adherence measures will be assessed at the IPL and at 6 months:

1. Wilson 3-item scale (self-report);
2. Viral load (HIV-1 RNA copies/mL).

Note: Hair samples will be tested following the 12-month visit, and will not be available for the primary analysis report or primary manuscript.

Safety Measures

The outcome measures for safety are the following youth adverse events:

1. Grade 2 or higher suicidal ideation or attempts;
2. Grade 3 or higher psychiatric disorder;
3. Grade 3 or higher insomnia.

4 Statistical Principles

4.1 General Considerations

Baseline characteristics will be summarized by arm, but there will be no statistical comparisons comparing arms because of the randomized study design. There are no planned interim efficacy analyses.

All statistical tests will be two-sided and will not be adjusted for multiple comparisons. Categorical data will be summarized using N (%) and continuous data using N, min, Q1, median, Q3, max, and mean (standard deviation (SD)) (when appropriate). Any modifications to outcome measures after the team has seen data that were collected after entry will be identified as such in the analysis report.

NIH requires the primary analyses of treatment comparisons to be summarized by sex and by race/ethnicity and that treatment interactions with sex/gender and race/ethnicity will be tested. It is expected that all participants will be Black Africans, therefore treatment interactions by race/ethnicity will not be performed unless that proves incorrect. Note, however, that the study has not been specifically designed to provide high power to evaluate treatment differences within subgroups or to evaluate treatment by subgroup interactions.

4.1.1 Analysis Populations

We define two analysis populations:

- Intention-to-treat (ITT): All randomized youth, regardless of receipt of their randomized intervention.
- Modified Intention-to-Treat (MITT): Randomized youth who were not enrolled in error, regardless of receipt of their randomized intervention.

All primary, secondary, and supplementary analyses will be conducted using the ITT analysis population, as indicated by Protocol Section 9.5. Supplementary analyses may additionally use the MITT analysis population, with greater detail and justification provided in Section 4.2.1.

4.1.2 Times Used in Primary and Secondary Outcome Measure Definitions

Baseline (pre-entry visit): The day baseline evaluations are completed (0-14 days prior to the Entry Visit).

Day 0 (entry visit): Day of enrollment, randomization, and Group Session 1.

Immediately post-last group session (IPL): Day of follow-up evaluation (0-30 days after Group Session 6).

6-month follow-up visit: Day 182 ± 30 days.

12-month follow-up visit: Day 365 ± 30 days (not included in this SAP).

4.2 Analysis Approaches

4.2.1 Analysis of the Primary Objective

The primary efficacy analysis will compare all primary outcome measures between randomized arms using the ITT analysis population. The primary outcome measures will be analyzed using a two-sided type I error rate of 0.05 and associated 95% confidence intervals in comparing differences between randomized arms. There will be no statistical adjustment for multiple comparisons. Only complete cases, i.e., youth with data for a specified measure, will be analyzed.

It is expected that the three mental health measures (PHQ-9, GAD-7, UCLA PTSD-RI) will be correlated; they will therefore be analyzed jointly using a composite measure. The three measures will first be standardized to the same scale, with mean 0 and standard deviation 1. Standardization will be done for each measure by subtracting the baseline (Pre-Entry) overall variable mean from each observation and dividing by the baseline pooled sample standard deviation. Resulting standardized scores thus represent the number of standard deviations from the baseline mean. Internal consistency of the mental health composite will be checked by examining Cronbach's alpha for the three standardized mental health measures to see if they form a coherent measure, indicated by an alpha greater than or equal to 0.70. If coherent, the composite mental health score will be created by summing the standardized scores within-youth.

The primary analysis comparing the composite mental health measure between arms will be a group-level analysis. One valid method for analyzing intervention effects within cluster randomized trials is to compute the mean for each cluster and then perform a t-test on the cluster-specific summaries. Here, a paired t-test will be performed for the difference in means between arms, with pairs defined by each distinct combination of site and wave. The same procedure will be used to analyze each mental health measure separately.

Supplementary Analyses

Group treatment results in correlated responses due to participant interactions with a shared group of facilitators and participants. Failure to account for this correlation can increase false positive (type I error) rates. Furthermore, each site may feature up to two waves (Figure 1). Within each wave, one group of participants receives experimental TI-CBT while the other receives Discussion Control. Waves are subsequent, rather than concurrent, and group leaders are common between waves and within site. Thus, wave may reflect temporality, e.g., treatment effects may change as leader experience increases, as well as between-group differences due to changes in group composition. Between-site heterogeneity is also expected. Multi-level models are commonly used to account for correlation within effect estimation, and also permit adjustment for wave and site, as well as additional covariates which can increase efficiency.

[figure not shown]

Figure 1. Structure of study site featuring two waves.

Supplementary analyses will be conducted separately for all primary outcome measures within the ITT analysis population using a multi-level model with two levels: individuals (level-1) nested within groups (level-2). Wave and site will be treated as fixed effects (i.e., adjusted for as covariates), along with other characteristics, as adjustment for strong prognostic factors can increase efficiency. Small-sample adjustment will be performed to ensure that inference is valid at the 5% significance level.

Potential covariates may include gender, number of sessions attended, caregiver participation, living situation (with or without parents), route of infection, and reported contamination between groups. Variable selection techniques will be used to identify candidate predictors strongly associated with each outcome among the ITT analysis population. Variables with $p < 0.20$ within single variable models will be considered candidates for the final adjusted model. Candidate predictors will be selected into the final model following discussion with the protocol team to confirm clinical relevance (or prior evidence) and exclude (or combine) one or more covariates if highly correlated or colinear.

The GAD-7 and PHQ-9 assessments are scorable for all youth, unlike the UCLA PTSD-RI (see Section 4.2.3). If more than 10% of UCLA PTSD-RI assessments are unscorable at the PCD, another supplementary analysis will repeat the primary analysis for an additional composite

mental health measure compromised only of the GAD-7 and PHQ-9, regardless of Cronbach's alpha.

To investigate sources and impacts of bias, primary analyses will also be repeated (1) within the MITT analysis population, described below; and (2) using imputed data, described in Section 4.2.3, rather than a complete case approach.

ITT analyses are the only analyses protected by randomization, i.e., both measured and unmeasured confounders will be balanced between randomized arms thus providing an unbiased treatment effect, and represent the analysis standard for RCTs. However, in the presence of multiple eligibility or enrollment errors, the ITT analysis population may not reflect the target analysis population of IMPAACT 2016. For example, mental health symptoms may be less severe than expected if youth were enrolled with mental health scores less than the eligibility thresholds (i.e., PHQ-9 \geq 10, GAD-7 \geq 10, UCLA PTSD-RI \geq 35). To assess the degree to which external generalizability of trial findings may be impacted by these protocol deviations, analysis will be repeated among the MITT analysis population which excludes them, and effects estimated among the ITT and MITT analysis populations will be compared. Hypothesized mechanisms for any observed differences between effects will be discussed in publications and presentations of trial results.

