The primary efficacy outcome is the score on a composite mental health score created by standardizing participants' scores on the three mental health measures and summing them (refer to [Section 9.5.1](#)). These scores will be standardized to all be on the same scale, with mean 0 and standard deviation 1 (173). For this reason, the power analysis uses number of standard deviations (effect size) to measure detectable differences between study arms. The sample size was chosen to provide 80% power to detect a clinically important difference in the primary efficacy measures between study arms. Power increases (allowing the detection of smaller effect sizes) when the number of groups increases, the ICC decreases, or (to a lesser extent) the average group size increases. The team will use two-sided tests to ensure power to detect differences between groups in both directions, but the hypothesis is that TI-CBT groups will lead to better mental health than the Discussion Control groups.

[Table 5](#) shows the detectable differences between arms with 80% power and two-sided  $\alpha = 0.05$  for a range of ICCs, numbers of groups per arm, and average numbers of participants per group. The study is expected to have 12-16 groups per arm with an average of 8 participants per group (allowing 6-10 per group), and thus, it is expected the total sample size will be 192-256 participants. This will provide 80% power to detect an effect size of 0.42-0.62 standard deviations between arms, or 0.47 - 0.65 if there is an average loss of 2 participants per group (an average group size of 6).

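### The Protocol sizes the trial on the composite, but the SAP tests four primary outcomes at 0.05 each, unadjusted, and never says which result decides

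*SAP*

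**What the plan says.** **Protocol.** Section 9.3.1 uses the singular: "The primary efficacy outcome is the score on a composite mental health score". It expresses power in standard deviations for that reason. Section 9.5.1 says that, because the three measures are expected to correlate, they are analysed as a composite for the primary analysis; the same procedure is then applied to each measure. Table 4 lists all four as primary outcome measures at 6 months, without ranking.

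**SAP.** Section 3.1 also lists the four without ranking: "The primary outcome measures used to address the study's primary objective are the following measures of mental health at 6 months after entry". Section 4.2.1 opens with "The primary efficacy analysis will compare all primary outcome measures between randomized arms using the ITT analysis population" and continues "The primary outcome measures will be analyzed using a two-sided type I error rate of 0.05 and associated 95% confidence intervals". It then states "There will be no statistical adjustment for multiple comparisons", which SAP 4.1 repeats for all tests. Each measure gets a paired t-test on group means, paired by site and wave. The composite is formed only if Cronbach's alpha is at least 0.70.

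**Objective.** SAP 2.3.1 asks whether TI-CBT is "associated with improved depression, anxiety, and/or traumatic stress symptoms". The hypothesis in SAP 2.2 and Protocol 1.4 has the same and/or form.

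Neither document gives a testing order, a gatekeeping step or a rule for declaring the primary objective met.

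**The concern.** Leaving several tests unadjusted is defensible when one of them is fixed in advance as decisive. The Protocol comes close to fixing one, but the SAP does not carry that into its testing plan. With four tests in the primary efficacy analysis and an and/or objective, a significant PHQ-9 with a null composite could be reported as meeting the primary objective, or as not meeting it, and the plan supports both readings.

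Such disagreement is realistic. Each measure is analysed on its own complete cases. SAP 4.2.3 treats unscorable UCLA PTSD-RI assessments as missing, and SAP 4.2.1 prepares for more than 10% of them. The composite may therefore rest on fewer youth than PHQ-9 or GAD-7.

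These outcomes define the primary analysis report, the primary publication and the registry posting (Protocol 9.2, SAP 1.1). Which result counts should not remain open until the results are known.

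**Working it through.** **1. Reproduce the plan's own figure.** Inputs from Protocol 9.3.1 and Table 5: m = 12-16 groups per arm, average size n = 8, ICC 0.05-0.15, two-sided 0.05, 80% power. Take SE = sqrt(2 × (1 + (n − 1) × ICC) / (m × n)) and a noncentral t with 2(m − 1) degrees of freedom.

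- m = 16, ICC 0.05: SE = sqrt(2 × 1.35 / 128) = 0.145. Power at 0.42 SD is 79.9%; the detectable difference is 0.421.
- m = 12, ICC 0.15: SE = sqrt(2 × 2.05 / 96) = 0.207. Power at 0.61 SD is 80.5%; the detectable difference is 0.606.

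The plan's range is reproduced (Table 5 prints 0.61 where the text prints 0.62). It is the sensitivity of **one** test at 0.05. The documents state no error rate for the set of four.

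**2. Correlation between the measures.** The documents say only that the measures are expected to correlate. I assume a common r of 0.4-0.7 and show higher values. The SAP's own condition gives a reference point: for three standardized items alpha = 3r / (1 + 2r), so alpha = 0.70 means r = 0.7 / 1.6 = 0.4375. At r = 0.4, alpha = 1.2 / 1.8 = 0.667, and the SAP would not form the composite.

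**3. Chance of at least one false positive.** Simulation with no true difference on any measure: three equally correlated pair differences plus their sum, a paired t-test on each at two-sided 0.05, and 12 or 16 pairs. The SAP's structure of eight sites with up to two waves gives at most 16. There were at least 150,000 trials per setting.

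| r | At least one of four, either direction | At least one of four, favouring TI-CBT |
|---|---|---|
| 0.4 | about 14.1% | 7.1% |
| 0.4375 | 13.8-13.9% | 6.9-7.0% |
| 0.5 | 13.3-13.5% | 6.7% |
| 0.6 | 12.4-12.6% | 6.2-6.3% |
| 0.7 | 11.3-11.6% | 5.7-5.8% |
| 0.8 | about 10.3% | 5.1% |
| 0.9 | about 8.6% | 4.3-4.4% |
| One test | 5.0% | 2.5% |

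The last column is about half the middle one because positively correlated tests rarely err in opposite directions in the same trial.

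**4. If alpha is below 0.70.** No composite is formed, and three unranked tests remain: about 13-14%.

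**5. Remedies compared.** With the composite as the single or gatekeeping test, the chance of a false primary claim is 5.0% and the detectable difference stays at 0.42-0.61 SD. With Bonferroni at 0.05 / 4 = 0.0125 on each test, the error rate for the set is 3.2-4.0% at r = 0.4-0.7. The detectable difference then rises to about 0.51-0.74 SD, and power at the design effect falls to about 60%.

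**The case against.** **The composite already has priority.** Protocol 9.3.1 and 9.5.1 put it first, and SAP 4.2.1 describes the composite comparison before saying that each measure is analysed in the same way. A reader might infer from the unranked lists that the plan gives four outcomes equal rank. The documents do not support that: an unranked list is not a statement of equal rank, and the text leans towards the composite. The lean is informal, however. SAP 4.2.1 still places all four in the primary efficacy analysis, and Protocol 9.3.1 and SAP 2.4 also speak of primary efficacy measures in the plural.

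**The error rate is not misstated.** A reader might infer that the SAP promises 5% overall and breaks the promise. It does not: it states a per-test rate, declares the lack of adjustment, and claims no rate for the set. The and/or wording is a hypothesis, not a decision rule. This stands. What remains is that no decision rule is given.

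**The size is conditional.** The 11-14% depends on an assumed correlation and counts errors in both directions; false claims of benefit are about half of it. The figure of 18.5% for four independent tests (1 − 0.95^4) cannot apply, because the composite is the sum of the other three.

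**Gatekeeping has a price.** PHQ-9 and GAD-7 are scorable for all youth, yet would wait behind a composite limited to youth with a scorable UCLA PTSD-RI. If benefit were confined to one domain, the composite could miss it. Both points stand as costs of the fix.

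**Conclusion.** The concern holds as a gap in the SAP. The Protocol's priority for the composite is not written into a testing order or a success rule, while four unadjusted tests serve an and/or objective. If the correlation between the measures is 0.4-0.7, the chance of at least one false-positive primary test under the global null is about 11-14%, of which about 6-7% favours TI-CBT, against 5% and 2.5% for one test. At 0.8-0.9 it is about 9-10%.

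These figures assume equal correlations, normal pair differences, the same youth contributing to every measure, and a correlation between group-mean differences like that between individual scores.

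This should be fixed. It does not invalidate the design or the sample size: the composite test on its own keeps its 5% rate and its stated power.

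**What to change.** In SAP 3.1 and 4.2.1:

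1. State that the composite at 6 months is the single primary test at two-sided 0.05, in line with Protocol 9.3.1 and 9.5.1.
2. Test PHQ-9, GAD-7 and UCLA PTSD-RI confirmatorily only if the composite is significant, by Holm or in a fixed order. Otherwise report them as estimates with 95% confidence intervals and no confirmatory claim.
3. Form and test the composite whatever Cronbach's alpha turns out to be, reporting alpha descriptively; or name now the primary test that applies if alpha is below 0.70. Without this, the single primary test could disappear and leave three unranked ones.

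**Cost.** No added sample size and no loss of power for the composite. A lone component result could no longer be claimed as primary success. The SAP edit is sufficient. Changing Protocol Table 4 is a protocol change that needs ethics review at the sites, so it can be aligned at the next amendment.
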